10. QUALITY MANAGEMENT

10.1 Site Set-up and Initiation

All sites will be required to sign a Clinical Study Site Agreement prior to participation. In addition all participating Investigators will be asked to sign the necessary agreements, registration forms and supply a current CV to the Trials Office. All members of the site research team will also be required to sign the Site Signature and Delegation Log, which should be returned to the Trials Office. Prior to commencing recruitment all sites will undergo a process of initiation. Key members of the site research team will be required to attend either a meeting or a teleconference covering aspects of the trial design, protocol procedures, AE reporting, collection and reporting of data and record keeping. Sites will be provided with an Investigator Site File and a Pharmacy File containing essential documentation, instructions, and other documentation required for the conduct of the trial. The Trials Office must be informed immediately of any change in the site research team.

10.2 On-site Monitoring

Monitoring will be carried out as required following a risk assessment and as documented in the TORCH Quality Management Plan. Additional on-site monitoring visits may be triggered for example by poor CRF return, poor data quality, low SAE reporting rates, excessive number of patient withdrawals or deviations. If a monitoring visit is required the Trials Office will contact the site to arrange a date for the proposed visit and will provide the site with written confirmation. Investigators will allow the TORCH trial staff access to source documents as requested.

10.3 Central Monitoring

Where a patient has given explicit consent sites are requested to send in copies of signed ICFs for inhouse review.

Trials staff will be in regular contact with the site research team to check on progress and address any queries that they may have. Trials staff will check incoming Case Report Forms for compliance with the protocol, data consistency, missing data and timing. Sites will be sent Data Clarification Forms requesting missing data or clarification of inconsistencies or discrepancies.

Sites may be suspended from further recruitment in the event of serious and persistent noncompliance with the protocol and/or GCP, and/or poor recruitment. Any major problems identified during monitoring may be reported to the Trial Management Group and Trial Safety Committee and the relevant regulatory bodies. This includes reporting serious breaches of GCP and/or the trial protocol to the main Research Ethics Committee (REC) and the Medicines for Healthcare products Regulatory Agency (MHRA).

10.4 Audit and Inspection

The Investigator will permit trial-related monitoring, audits, ethical review, and regulatory inspection(s) at their site, providing direct access to source data/documents.

Sites are also requested to notify the Trials Office of any MHRA inspections.

10.5 Notification of Serious Breaches

In accordance with Regulation 29A of the Medicines for Human Use (Clinical Trials) Regulations 2004 and its amendments the Sponsor of the trial is responsible for notifying the licensing authority in writing of any serious breach of:

- The conditions and principles of GCP in connection with that trial or;
- The protocol relating to that trial, within 7 days of becoming aware of that breach

For the purposes of this regulation, a "serious breach" is a breach which is likely to effect to a significant degree:

- The safety or physical or mental integrity of the subjects of the trial; or
- The scientific value of the trial

Sites are therefore requested to notify the Trials Office of a suspected trial-related serious breach of GCP and/or the trial protocol. Where the Trials Office is investigating whether or not a serious breach has occurred sites are also requested to cooperate with the Trials Office in providing sufficient information to report the breach to the MHRA where required and in undertaking any corrective and/or preventive action.

11. END OF TRIAL DEFINITION

The end of trial will be 6 months after the last data capture. This will allow sufficient time for the completion of protocol procedures, data collection and data input. The Trials Office will notify the MHRA and main REC that the trial has ended and will provide them with a summary of the clinical trial report within 12 months of the end of trial.

12. STATISTICAL CONSIDERATIONS

12.1 Definition of Outcome Measures

12.1.1 Primary outcome measures

• Best overall response rate during the first 6 cycles of AZD2014 will be assessed using contrast-enhanced CT scans of the neck, chest, abdomen and pelvis, using the Revised Response Criteria for Malignant Lymphoma.

12.1.2 Secondary outcome measures

- Best overall response rate post 6 cycles until the end of the trial, assessed using the revised Response Criteria for Malignant lymphoma (Appendix 1)
- Tolerability of AZD alone and in combination with rituximab will be assessed using Toxicities recorded during trial treatment using CTCAE v4.0
- Progression free survival is defined as the time from date of registration to the date of disease progression or date of death from any cause. Patients not reaching progression or death at the time of analysis will be censored at the last date they were known to be alive and progression free. Patients will be followed up for a minimum of 12 months.
- Overall survival time is defined as the time from date of registration to the date of death from any cause. Patients discontinuing the study, lost to follow-up or still alive at the end of the study will be censored at the date of last follow-up. Patients will be followed up for a minimum of 12 months. Duration of response is defined as the time from first documented response until relapse/progression, as determined by the Revised Response Criteria, or date of last follow up if relapse/progression free. Patients who die before a relapse/progression will be censored at their date of death.
- Maximum % decrease in the radiological SPD during the first 6 cycles will be assessed using the Revised Response Criteria for Malignant Lymphoma (Appendix 1) using the CT scan result collected at screening as a baseline value.

Exploratory Outcome Measures

- Correlation of response with pharmacodynamic biomarkers, cell of origin studies, lymphoidrelated mutational analysis and potential predictive biomarkers of response
- To determine the response to AZD2014 by PET CT criteria and analyse the effect of dual mTOR inhibition on PET signal / response when compared to standard CT response

Pre and post treatment biopsies (at subsequent relapse) will be performed to measure relative activity of the mTOR pathway in a biomarker exploratory analysis. Biopsies at relapse will be requested in patients within the rituximab stage to assess for evidence of synergy and mechanisms of resistance. On treatment biopsies on day 15 cycle 1 will remain optional.

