7.9 Treatment discontinuation and Patient Withdrawal

In the event of discontinuation of study treatment, e.g. unacceptable toxicity or patient choice, full details of the reason/s for discontinuation should be recorded on the appropriate pages on the CRF. All patients, including non-compliant subjects, should be followed up according to the protocol unless they withdraw specific consent.

In the event of a patient's decision to withdraw from the trial, the Investigator should ascertain from which aspects of the trial the patient wishes to withdraw and record the details on the appropriate

CRF. If a patient chooses to withdraw from treatment only, the patient should discontinue treatment and continue to be assessed in accordance with the protocol.

If a patient wishes to withdraw from the trial (i.e. including trial specific assessments), but is willing for further data to be supplied to the Trials Office, then further routine "follow-up" data (e.g. disease status and survival) will continue to be supplied by the Investigator to the Trials Office. All information and blood/tissue samples collected up until point of retraction will be retained and analysed.

Patients who stop treatment due to AEs (clinical or laboratory) will be treated according to accepted medical practice and followed up as per protocol. All pertinent information concerning the outcome of such treatment must be recorded in the CRF.

The following are justifiable reasons for the Investigator to stop study treatment:

- unforeseen events: any event which in the judgement of the Investigator makes further treatment inadvisable
- serious violation of the study protocol (including persistent patient non-attendance and persistent non-compliance)
- stopping by the Investigator for clinical reasons not related to the study drug treatment

Patients must stop study treatment in the event of:

- SAE requiring permanent discontinuation of treatment
- the patient becoming pregnant
- Clinically significant ECG changes
- Interstitial lung disease
- Stevens-Johnson syndrome, Progressive multifocal Leukoencephalopathy or other significant infusion related reactions

If trial treatment is discontinued the patient must attend clinic for the end of treatment visit and 30 days (+/- 5 days) after their last trial treatment for the 30 days post treatment visit, unless they have withdrawn consent for these assessments.

End of treatment visit assessments

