- Clinical assessment to include vital signs (heart rate, systolic and diastolic BP, oxygen saturation (pulse oximetry), weight, and temperature
- Constitutional symptoms will include , night sweats and recurrent fever ≥38.0°C,
- Laboratory tests to include full blood counts, Standard biochemistry including glucose, Hba1c, triglycerides and cholsterol⁻
- ECG
- PET-CT to include contrast enhanced CT (if Progression only)
- ECOG
- Con meds
- AEs

30 days post treatment assessments (+/- 5 days)

- Clinical assessment to include vital signs (heart rate, systolic and diastolic BP, oxygen saturation (pulse oximetry), , weight, and temperature
- Laboratory tests to include full blood counts, Standard biochemistry inclusing glucose, Hba1c, triglycerides and cholsterol
- ECOG
- AEs

Following study treatment discontinuation the patient should be treated at the Investigator's discretion.

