8.1.3 Reporting period

Details of all AEs (except those listed above) will be documented and reported from the date of commencement of protocol defined treatment until 30 days after the administration of the last treatment.

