8.2 Reporting Procedure

8.2.1 Site

8.2.1.1 Adverse Events

AEs should be reported on an AE Form (and where applicable on an SAE Form). An AE Form should be completed at each visit and returned to the Trials Office.

AEs will be reviewed using the CTCAE, version 4.0 (see Appendix 6). Any AEs experienced by the patient but not included in the CTCAE should be graded by an Investigator and recorded on the AE Form using a scale of (1) mild, (2) moderate or (3) severe.

For each sign/symptom, the highest grade observed since the last visit should be recorded.

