12.2 Analysis of Outcome Measures

- Best overall response will be reported as the number and proportion of patients in each response category, and overall, during the first 6 cycles of treatment. In addition, best response observed after 6 cycles until the end of the trial will be reported by category and overall.
- The number and proportion of patients experiencing toxicity, including haematological and nonhaematological toxicity, will be reported with 95% confidence intervals.
- Time to event outcomes will be assessed using the method of Kaplan and Meier with point estimates presented at 6, 12, 24 and 36 months with 95% confidence intervals along with median survival time and confidence intervals. A Kaplan meier plot will be produced.
- The mean maximum % decrease during the first 6 cycles of treatment and overall will be reported with 95% confidence intervals

The biomarker study and PET scan analysis at present are exploratory.

There is little data on the expression of mTOR pathway proteins in DLBCL so the aim is to define expression in biopsy samples taken at relapse (or within 3 months). In collaboration with AstraZeneca, we will assess the expression of these proteins (p-S6, p-AKT, and p-4E-BP1) by immunohistochemistry (IHC). These will be measured at relapse, at subsequent progression, and in any tissue obtained at further optimal biopsy at 15 days. This will be initially assessed in 8 patients, with the potential to expand the analysis dependent on response data. We will then seek to determine a cut off which best predicts response to AZD2014, if indeed there is any correlation. Appropriate

statistical models (e.g. area under the curve, logistic regression) will be used to determine the cut off as detailed in the Statistical Analysis Plan.

Other ethically approved research may be performed on these samples if agreed by the trial management group.

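### The tolerability outcome in 12.1.2 is limited to toxicity recorded during treatment, a shorter window than the AE collection period in 8.1.3, which runs to 30 days after the last treatment

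*Protocol*

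**What the plan says.** Protocol section 12.1.2, under the heading for definitions of outcome measures, says: "Tolerability of AZD alone and in combination with rituximab will be assessed using Toxicities recorded during trial treatment using CTCAE v4.0". No post-treatment period is mentioned.

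Section 8.1.3 sets the collection period for AEs: they "will be documented and reported from the date of commencement of protocol defined treatment until 30 days after the administration of the last treatment". Section 7.9 has the patient attend "30 days (+/- 5 days) after their last trial treatment for the 30 days post treatment visit", and AEs are on the list of assessments for that visit. Section 8.2.1.1 adds: "An AE Form should be completed at each visit and returned to the Trials Office". The grade entered on the form is the highest since the previous visit, so the post-treatment form covers the interval after stopping.

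Section 12.2 gives the analysis: "The number and proportion of patients experiencing toxicity, including haematological and nonhaematological toxicity, will be reported with 95% confidence intervals". It states no time window.

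Section 12.6 has a separate tolerability decision rule. It counts toxicities that cause a treatment delay or dose modification in the first two cycles.

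**The concern.** The trial collects a 30-day tail of safety data that its own outcome definition does not cover. Section 12.2 analyses what section 12.1 defines, and it has no window of its own. A programmer who follows the text would therefore take the on-treatment window, which is the only one stated. Another could take the full collection period. The two would report different toxicity rates from the same data.

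The tail is unlikely to be neutral. Table 2 in section 7.5.1 holds the drug for certain grade 3 or 4 toxicities and discontinues it if they persist beyond 14 days. For those patients the last dose comes about two weeks or more before the decision to stop, and 12.1.2 does not say which of the two ends the treatment period. Section 7.9 also requires stopping for events such as interstitial lung disease, whose worst grade may come later.

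At stake are the descriptive toxicity proportions and any summary of maximum grade. This includes the six-patient combination stage, whose stated purpose is to assess additional toxicity.

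**Working it through.** **1. The windows side by side**

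| Source | Window |
|---|---|
| 12.1.2, outcome definition | during trial treatment |
| 8.1.3, AE collection | start of treatment to 30 days after last treatment |
| 7.9 and 7.3, post-treatment visit | 30 ± 5 days, i.e. day 25 to day 35 |
| 12.2, reported proportions | none stated |
| 12.6, decision rules | first two cycles |

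The mismatch is between the first two rows, and the fourth does not resolve it.

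**2. Direction.** With a fixed number of patients, lengthening the window can add patients to the numerator or raise a maximum grade. It cannot do the reverse. Any omission therefore lowers the reported figures.

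**3. The decision rule, reproduced first.** Inputs from 12.6: at least 10 of 15 tolerable, then at least 21 of 30; unacceptable rate 60%, acceptable rate 80%.

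P(conclude tolerable) = Σ over x = 10 to 15 of C(15,x) pˣ(1−p)¹⁵⁻ˣ × P(Y ≥ 21−x), with Y ~ Bin(15, p).

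- p = 0.8: 0.9049 (protocol 90.4%)
- p = 0.6: 0.1521 (protocol 15.3%, a difference of 0.1 point)
- Early stopping at p = 0.6, P(X ≤ 9): 0.5968 (protocol 59.7%)

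None of these depends on the descriptive window, because 12.6 fixes its own event and period. They are the same after the correction. The combination-stage rules (2 of 3, then 4 of 6) also count only the first two cycles.

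**4. Size of the effect on the descriptive rates.** The protocol gives no proportion of patients with first onset after stopping, so the effect cannot be computed. For scale only, let r be the on-treatment rate and q the assumed proportion of the remaining patients who first have the toxicity within 30 days of stopping. The full-window rate is r + (1−r)q, and the extra patients out of 30 number 30(1−r)q.

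| r | q = 2% | q = 20% |
|---|---|---|
| 40% | 41.2% (0.4 more patients) | 52.0% (3.6 more) |
| 80% | 80.4% (0.1 more) | 84.0% (1.2 more) |

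In the combination stage, one additional patient of six moves a proportion by 1/6, or 17 percentage points. Section 1.2.3.2 says the common AEs were generally reversible within a week of stopping. That points to small q for those events but says nothing about late-onset ones.

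**The case against.** The best defence is that the protocol nowhere says post-treatment toxicities are left out. The word *only* does not appear in 12.1.2. The lists of outcome measures in the synopsis and in 2.2 give no window, and 12.2 gives none either. The exact window for safety tables is often left to an SAP. This stands in part: exclusion is a reading of the text and not an explicit rule. But 12.1.2 does state a window, and that window conflicts with 8.1.3. An SAP would have to inherit it or depart from it.

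It is also fair that the outcome is secondary and descriptive, and that no go/no-go rule changes. Both points stand.

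Three stronger inferences are tempting and are not supported:

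- *A visit on day 25 leaves AEs on days 26 to 30 uncollected.* Section 8.1.3 requires reporting to day 30 whatever the visit date. The schedule in 7.3 lists AEs throughout the study, with a clinical assessment at three-monthly follow-up, and its notes have unresolved adverse reactions and SAEs monitored further. The visit may also fall as late as day 35.
- *About a fifth of the safety data is lost.* With the 2.6-month median PFS from section 1.1 and exponential treatment times, mean treatment is 2.6/ln 2 = 3.75 months, or 114 days, and the tail is 30/(114 + 30) = 21% of collection time. That PFS comes from another study and is not time on treatment. A share of time or events is also not a proportion of patients: someone who already had the toxicity on treatment is counted either way.
- *The combination-stage decision is biased.* Its rule uses the two-cycle count, which is untouched.

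**Conclusion.** The concern holds as an inconsistency of wording: the outcome window in 12.1.2 is narrower than the collection period in 8.1.3, and 12.2 does not settle which applies. If the definition is followed as written, toxicities that arise or peak after the last dose are collected but not reported under this outcome. The error can go only one way, towards lower toxicity. This conclusion assumes that 12.2 takes its window from 12.1.2.

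The protocol does not allow the size to be derived. The figures under the assumed 2% to 20% late onset show scale and are not estimates. The tolerability decision rules keep their operating characteristics. Severity: minor.

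**What to change.** In 12.1.2, replace the restriction to toxicities recorded on treatment with: *recorded from the first dose until 30 days after the last trial treatment*. State in 12.2 that the toxicity proportions use the same window. Leave the cycle 1-2 count in 12.6 unchanged.

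The window should not be cut short at the start of new anti-lymphoma therapy. Section 8.1.3 has no such limit, so adding one would create a fresh mismatch between what is collected and what is analysed. No change to the visit window is needed.

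The cost is a protocol wording change. The data are already within the collection period, and no sample-size or power figure moves. Reported toxicity rates may look slightly less favourable.

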- Determine the toxicity of single agent AZD2014 in patients with relapsed/refractory DLBCL.
- Evaluate any additional toxicities when rituximab is combined with AZD2014 at its standard dose (stage 2 only).
- Determine the impact on survival (as measured by progression free survival (PFS), overall survival (OS) and duration of remission (DoR)).
- Identify biomarkers of mTOR activity in DLBCL and of response to AZD2014.
- Identify possible resistance mechanisms to AZD2014.
- To determine the response to AZD2014 by PET CT criteria and analyse the effect of dual mTOR inhibition on PET signal/response when compared to standard CT response.
- To identify whether interim PET signal correlates with PFS.

Outcome Measures

Primary Outcome Measures

• Best overall response rate (PR plus CR) (using the Revised Response Criteria for Malignant Lymphoma, Appendix1) during the first 6 cycles

Secondary Outcome Measures

- Tolerability rate (based on toxicity assessments using CTCAE v 4.0 criteria) of single agent AZD2014
- Tolerability rate of additional toxicities when rituximab is combined with AZD2014 at its standard dose (stage 2 only)
- Best overall response rate post 6 cycles until the end of the trial, assessed using Revised Response Criteria
- Overall survival (OS) at 1 year
- Progression free survival (PFS) at 1 year
- Duration of response
- Maximum % decrease in the radiological sum of the product of the diameters (SPD) from baseline by CT NCAP

Exploratory Outcome Measures

- Correlation of response with pharmacodynamic biomarkers, cell of origin studies, lymphoidrelated mutational analysis and potential predictive biomarkers of response
- To determine the response to AZD2014 by PET CT criteria and analyse the effect of dual mTOR inhibition on PET signal / response when compared to standard CT response

Pre and post treatment biopsies (at subsequent relapse) will be performed to measure relative activity of the mTOR pathway in a biomarker exploratory analysis. Biopsies at relapse will be

requested in patients within the rituximab stage to assess for evidence of synergy and mechanisms of resistance. On treatment biopsies on day 15 cycle 1 will remain optional.

Patient Population

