12.6 Power Calculations

The sample size calculation is based on A'Hern's single stage phase II design. A total of 30 patients will be recruited in the main section of the study.

Activity

The treatment will be considered for further investigation if at least 9 responses are seen from the 30 patients. This results in 90% power to go forward if the underlying response rate is 40%, but only a 13% risk of going forward if the true response rate is 20% or less.

Toxicity

A Simon 2 stage design is proposed, using tolerability (i.e. opposite of toxicity) as the outcome.

A tolerability rate of 60% would not be acceptable, a tolerability rate of 80% would be.

The study would need to observe at least 10 'tolerable' outcomes (i.e. at most 5 toxicities that lead to treatment delays or dose modifications during the first 2 cycles) from the first 15 patients, and at least 21 'tolerable' outcomes (i.e. .at most 9 toxicities that lead to treatment delays or dose modifications

during the first 2 cycles) from the overall 30 to conclude that the treatment was tolerable at the current dose. This gives 90.4% power to conclude that treatment is tolerable when it is, but a 15.3% risk of concluding that the treatment is tolerable, when in fact it is not. If the treatment is too toxic then there is a 59.7% chance of stopping the trial at the halfway point.

For the combination stage at least 2 tolerable outcomes (i.e. at most 1 toxicity that leads to a treatment delay or dose modifications) during the first 2 cycles from the first 3 patients would need to be observed to continue recruitment. 4 tolerable outcomes (i.e. at most 2 toxicities that lead to treatment delays or dose modifications) are required during the first 2 cycles for the overall 6 to conclude that the combination treatment was tolerable at the current dose.

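### Duration of response censors responders at death, so its Kaplan-Meier curve estimates neither time alive in response nor the incidence of relapse

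*Protocol*

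**What the plan says.** The DoR definition is in Protocol Section 12.1.2: "Duration of response is defined as the time from first documented response until relapse/progression, as determined by the Revised Response Criteria". Patients free of relapse or progression are censored at last follow-up. On deaths the section adds: "Patients who die before a relapse/progression will be censored at their date of death". In the same section, PFS runs from registration "to the date of disease progression or date of death from any cause", so death is an event for PFS.

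Section 12.2 names the estimator: "Time to event outcomes will be assessed using the method of Kaplan and Meier with point estimates presented at 6, 12, 24 and 36 months". It also asks for medians with confidence intervals. No competing-risk method is named for any outcome.

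The purpose of the outcome is given among the secondary objectives of the Trial Synopsis: "Determine the impact on survival (as measured by progression free survival (PFS), overall survival (OS) and duration of remission (DoR". I take duration of remission there and duration of response in the outcome lists to be the same quantity. Nothing else in the protocol counts death as a DoR event or gives a reason for censoring it.

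**The concern.** Kaplan-Meier handles a censored patient as someone who stays at risk, with the same later hazard as those still under observation. That is reasonable for a responder who is alive at the data cut. It is not reasonable for one who has died, because death rules out relapse. With deaths censored, the curve describes relapse in a hypothetical population in which nobody dies first.

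A responder who dies before documented progression has therefore failed for PFS but not for DoR, although the protocol uses both to judge impact on survival. Few patients will contribute: the design rates of 20% and 40% in 30 patients give 6 to 12 expected responders, so one or two deaths can move the estimates visibly. Section 1.2.3 describes remissions with earlier mTOR inhibitors as short, so readers are likely to set this trial's DoR against those figures.

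**Working it through.** **The plan's own figures.** The protocol states no expected DoR, so there is none to reproduce. The activity rule in Section 12.6, which sets the number of responders, does reproduce. With at least 9 responses in 30, the exact binomial tail is 0.129 at a 20% response rate and 0.906 at 40%. This agrees with "13% risk of going forward if the true response rate is 20% or less" and "This results in 90% power to go forward if the underlying response rate is 40"%. That rule does not use DoR.

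**Inputs for the illustration**

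- Median time from response to relapse or death: m = 8.1 months. Section 1.2.3 cites this for everolimus plus rituximab. The protocol does not say whether that figure counted death, so treating it as the median with death counted is an assumption.
- Share of first events that are deaths without prior progression: s. The protocol does not give it. I use 0% to 30%, constant over time.
- Exponential times, an assumption.

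**Formulas**

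- Total hazard h = ln 2 / 8.1 per month.
- Alive and in response at t: exp(−ht). At 12 months this is exp(−12 ln 2 / 8.1) = 35.8%.
- Kaplan-Meier with deaths censored: exp(−(1−s)ht), with median 8.1/(1−s).
- Cumulative incidence of relapse: (1−s)(1−exp(−ht)).

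**Results at 12 months** (alive and in response is 35.8% in every row)

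| s | Median as reported (months) | KM, deaths censored | 1−KM | Relapse incidence |
|---|---|---|---|---|
| 0% | 8.1 | 35.8% | 64.2% | 64.2% |
| 10% | 8.1/0.9 = 9.0 | 39.7% | 60.3% | 57.8% |
| 20% | 8.1/0.8 = 10.1 | 44.0% | 56.0% | 51.4% |
| 30% | 8.1/0.7 = 11.6 | 48.7% | 51.3% | 44.9% |

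At s = 20% the curve reads 44.0% when 35.8% are alive and in response. Its complement reads 56.0% when 0.8 × 64.2% = 51.4% have relapsed. Both gaps vanish only at s = 0.

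**Small samples.** I simulated 9 and 12 responders, 5,000 runs each, with every first event observed. Counting death, the mean 12-month estimate was 0.354 to 0.362. Censoring deaths at s = 10%, 20% and 30%, it was 0.397, 0.443 and 0.485 with 9 responders, and 0.399, 0.445 and 0.488 with 12. In no run did censoring deaths lower the 12-month estimate.

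**Example by hand.** Take 12 responders with first events at months 1 to 12, those at months 3 and 6 being deaths.

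- Death counted: the 6-month estimate is 6/12 = 0.50 and the median is 6 months.
- Death censored: (11/12)(10/11)(8/9)(7/8) = 0.648 at 6 months. Month 7 multiplies by 5/6, giving 0.540, and month 8 by 4/5, giving 0.432. The median is 8 months.

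**The case against.** The strongest case against the point is that little hangs on it. DoR is one of seven secondary outcome measures. The activity decision rests on response counts alone ("The treatment will be considered for further investigation if at least 9 responses are seen from the 30 patients"), and tolerability has its own rule. The deaths are not hidden either, since PFS counts them and OS is reported. The censoring rule is stated openly, and two endpoints may legitimately treat death differently. Precision is also poor: with 12 observed exponential events, an approximate 95% interval around 8.1 months is 8.1 × exp(±1.96/√12), or 4.6 to 14.3 months, which contains every shifted median in the table. All of this stands, and it limits the severity. It does not make the estimate right: PFS starts at registration and OS ignores progression, so neither gives a corrected DoR for the responders.

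A second defence is that relapse alone was intended. That does not rescue the analysis, because 1−KM is biased for that target too.

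Some stronger readings are tempting but are not supported:

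- A reader might infer that the bias always flatters the drug. That holds for time alive in response. If relapse incidence is the target, 1−KM overstates relapse and counts against the drug.
- A reader might infer that deaths without documented relapse are mostly missed progressions. The protocol gives no such figure. CT is every 2 cycles to cycle 6 and then every 4 (112 days), or every 3 to 4 months off treatment in the first year, with extra scans on clinical suspicion (Sections 7.3 and 7.3.4). Missed progression is possible, but its frequency is unknown.
- The median overall survival of 7.2 months in Section 1.1, from a cited mTOR-inhibitor cohort, shows that mortality is high. It does not give the share of responders who die before progressing.

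**Conclusion.** The point holds. The censoring rule is explicit, current text, and combined with plain Kaplan-Meier it gives a curve that is too high for time alive in response and a complement that is too high for relapse incidence. The direction of each bias needs no numerical assumption. The size does. The medians of 9.0 to 11.6 months and the 12-month values of 40% to 49%, against 8.1 months and 36%, rest on exponential times, a median taken from another regimen and an assumed 10% to 30% share of deaths. With no such deaths the effect is nil. A reader might take 8.1 months and 36% as the expected result of this trial; they are only a scale for the illustration.

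A reader might also infer that the trial's conclusions are at risk. They are not: the primary response rule, the tolerability rule and the sample size are unaffected. The rating is should-fix.

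**What to change.** In Section 12.1.2, define DoR as the time from first documented response to relapse, progression or death from any cause, whichever comes first, and delete the sentence that censors deaths. Censor responders who are alive and progression-free by the same rule as PFS, at the last date they were known to be so. If relapse alone is the target, say so and report the cumulative incidence of relapse with death as a competing event. The death-censored curve can then be kept as a labelled sensitivity analysis.

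This needs no new data, since dates of response, progression and death are already required. The cost is a short text change and possibly a shorter reported DoR. It should be settled before results are seen, because with so few responders a later choice could turn on one or two deaths.
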